## **10.7 Death of a Study Participant**

As soon as Clinic personnel become aware that a Study Participant has died, a Study Termination Form must be completed and forwarded to the DCC.

## **10.8 Special Problems in Follow-up**

Every effort should be made to maintain the follow-up visit schedule outlined in Table 10.1 for each Study Participant. However, during the course of the trial particular Study Participants may develop special problems that require some individualization of the procedures. Problem participants include those who move from the area of the Clinical Center, participants who are called to active duty and deployed, or those who become debilitated and cannot return to the Clinical Center. One important principle should be kept in mind in determining the management of these Study Participants. Even if a Study Participant should become inactive, every effort should be continued to reinstate him or her to active status. Maximum possible contact between Study personnel and the Study Participant should be maintained until the Study Participant dies or the study is terminated.

If, for any of the reasons discussed above, a Study Participant cannot reasonably be expected to return for every scheduled study visit, then the Clinical Center Director should review the participant's situation and make an alternative plan for completing each follow-up visit. It may be possible to transfer the Study Participant to another Clinical Center, arrange special transportation for the Study Participant, or conduct a Study Visit at another location. At the very least, Study Participants should be requested to complete the questionnaires evaluating tinnitus intrusiveness and annoyance (Tinnitus Questionnaire, Tinnitus Functional Index, and Tinnitus Handicap Inventory) by sending a paper copy of the form to the Study Participant along with a pre-posted return envelope.

---

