#### **9.3.2.1 Beck Depression Inventory Fast Screen**

The Beck Depression Inventory (Beck, Brown, and Steer, 1996) is the most widely used measure of depressive symptoms. The original inventory had 21 items, employed a 4-point Likert scale of 0-3 for each response item, and could be completed in approximately 10 minutes. The areas of assessment relate to cognitive, affective, and somatic symptoms. The Beck Depression Inventory has been used in scores of outcome studies examining treatment effectiveness with both clinical and non-clinical populations. A more recent version, the Beck Depression Inventory II, was revised specifically to conform with two-week criterion for symptom duration described in the Diagnostic and Statistical Manual, 4th Edition (DSM-IV). In addition, a 7 item version, the Beck Depression Inventory Fast Screen (or Quick Screen) was introduced with comparable psychometrics to the original version ( Benedict, *et al.*, 2003). We will use the Beck Depression Inventory Fast Screen in the TRTT.

The Beck Depression Inventory Fast Screen will be completed during the Baseline Eligibility Visit to determine whether the individual should be further evaluated for depression. The threshold score on the Beck Depression Inventory Fast Screen for determining the need for

further evaluation is a score  $\geq 4$  or endorsement (a response of 2 or 3) on item # 7 (suicidal thoughts or wishes). The Clinical Center Director must take appropriate steps with respect to requesting or scheduling an appropriate consultation for individual failing the screen. Following professional evaluation, individuals who have not passed the screen may be evaluated for eligibility for participation in the TRTT. Repeated measures of the Beck Depression Inventory Fast Screen over the course of the TRTT will permit Study Participants to be monitored for onset of serious depression as a possible consequence of treatment or other contributing factors. The TRTT will define the same threshold - a score of 4 or greater on the Beck Depression Inventory Fast Screen or endorsement of item # 7 (suicidal thoughts or wishes) - as an adverse event. The Clinical Center Director is responsible for referring the Study Participant to an appropriate health care provider in this circumstance.

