#### **10.4.2 Inactive Study Participants**

Any Study Participant who has missed two consecutive visits is considered to be inactive, or lost to follow-up until she or he is seen by a study staff member for a complete study visit and is reinstated. The Clinical Center staff is not relieved of responsibility for "inactive" Study Participants. On the contrary, such Study Participants generally require much more staff time than those following the regular schedule. The requirements for managing inactive Study Participants are:

- The Study Participant should be contacted at least every three months. At this time, his or her situation should be reviewed, and if possible, arrangements should be made for him or her to return to the Clinical Center;
- If possible, the Study Participant will be requested to complete the self-test instruments using paper forms that can be mailed to him or her.
- If a Study Participant cannot be located, it is the responsibility of the Clinical Center Director to notify the Study Chair in writing, reviewing in detail the Study Participant's situation and the measures that have been taken to assure adequate

follow-up. The Steering Committee reviews the Study Participant's record and formulates recommendations for action to be taken.

- It is the responsibility of the Clinical Center Director to send written notification to the Study Chair (and a copy to the Director of the Data Coordinating Center (DCC)) outlining the steps taken to locate the Study Participant.

Every effort should be made to encourage an inactive Study Participant to return. If an inactive Study Participant is persuaded to resume clinic visits, the follow-up visit indicated on the Appointment Schedule (as appropriate for that time period) should be completed for this Study Participant. Receipt by the DCC of a Follow-up Visit form completed by Clinical Center staff automatically removes the Study Participant from the inactive category.

All pertinent facts concerning the interim history since the participant's last completed Follow-up Visit should be summarized under the appropriate items on the first Follow-up Visit form which is completed following reinstatement.

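### The minimum remote data set in section 10.8 does not require the Beck Depression Inventory Fast Screen, although section 9.3.2.1 makes its threshold an adverse event

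*Combined protocol and SAP*

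**What the plan says.** Section 9.3.2.1 gives the BDI-FS a safety role after baseline: repeated measures "will permit Study Participants to be monitored for onset of serious depression as a possible consequence of treatment" or of other factors. It then sets the event definition, first on the total: "The TRTT will define the same threshold - a score of 4 or greater on the Beck Depression Inventory Fast Screen". A second criterion counts on its own, whatever the total: "endorsement of item # 7 (suicidal thoughts or wishes) - as an adverse event". Crossing the threshold also obliges the Clinical Center Director to refer the participant.

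Section 10.3 and Table 10.2 schedule the BDI-FS at 3, 6, 12 and 18 months. Section 2.2.3 also lists change in BDI-FS among the health-related outcomes.

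Two sections deal with people who do not come to the clinic.

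- Section 10.8 covers participants who move, are deployed or become debilitated. The Clinical Center Director is to "make an alternative plan for completing each follow-up visit". The options are transfer to another center, or to "arrange special transportation for the Study Participant, or conduct a Study Visit at another location". If those fail, the floor is: "At the very least, Study Participants should be requested to complete the questionnaires evaluating tinnitus intrusiveness and annoyance". The instruments are then listed: "Tinnitus Questionnaire, Tinnitus Functional Index, and Tinnitus Handicap Inventory) by sending a paper copy of the form to the Study Participant".
- Section 10.4.2 covers inactive participants, meaning those with two consecutive missed visits. If possible, "the Study Participant will be requested to complete the self-test instruments using paper forms that can be mailed to him or her". It does not list the instruments.

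**The concern.** This adverse event is defined by an instrument score. If the instrument is not completed, the event cannot be ascertained as defined. The 10.8 floor leaves out the one form on which it depends. It also leaves out the Follow-up Medical History Form, which is due at the same visits, so a participant handled at the floor supplies neither.

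The trial runs in military centers and enrolls active-duty personnel, and 10.8 itself expects deployment and debilitation. Two things are at stake: the completeness of depression monitoring in people who are hard to reach, and the clarity of the event rates that the Data and Safety Monitoring Board sees. A rate shown without the number assessed does not reveal how many people were never screened.

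**Working it through.** The plan gives no figure on this point, so there is nothing to reproduce. The check is textual, followed by an illustration of scale.

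**Which rule applies to whom**

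- One missed visit because of deployment, a move or debility: only 10.8 applies. The floor is the Tinnitus Questionnaire, Tinnitus Functional Index and Tinnitus Handicap Inventory.
- Two consecutive missed visits for the same reason: 10.4.2 applies as well. Chapter 9 treats the BDI-FS as a self-report measure, so the wording of 10.4.2 can include it. The same person then falls under two differently worded mailed sets.
- Midpoint telephone calls (10.5.2) reach everyone, and inactive participants are contacted at least every three months (10.4.2). Neither section specifies a depression screen for these contacts.
- After 18 months, 10.3 drops the BDI-FS for all participants. The gap specific to non-attenders is therefore confined to the 3, 6, 12 and 18 month visits.

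Nothing in the chapters available requires a BDI-FS from a participant handled only at the 10.8 floor.

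**Illustration of scale at one visit**

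Inputs: N = 228 (section 2.3). The share at the floor, f, and the share crossing the threshold, p, are not given. They are assumed here as f = 5%, 10% and 20%, and p = 5% to 30%.

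Participants with a missed event = 228 × f × p:

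- f = 5%: 228 × 0.05 × 0.05 = 0.6, to 228 × 0.05 × 0.30 = 3.4
- f = 10%: 228 × 0.10 × 0.05 = 1.1, to 228 × 0.10 × 0.30 = 6.8
- f = 20%: 228 × 0.20 × 0.05 = 2.3, to 228 × 0.20 × 0.30 = 13.7

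**Effect of the denominator**

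- Same p in everyone, p = 20%, f = 10%. If unassessed people were counted as event-free, the rate would be 0.20 × (1 − 0.10) = 18%. With the number assessed as denominator it is 20%, which is correct.
- Higher p in those not screened: 20% in attenders and, by assumption, 40% in the rest, with f = 10%. Events seen are 228 × 0.90 × 0.20 = 41.0 and events missed are 228 × 0.10 × 0.40 = 9.1. The missed share is 9.1 / 50.2 = 18%. The true rate is 50.2 / 228 = 22%, while the assessed-only rate is 20%.

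The right denominator makes the gap visible. Only collecting the form closes it when those not screened differ from the rest.

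**The case against.** The 10.8 list is a floor. Before it come transfer, transportation or a visit elsewhere, and a completed visit includes the BDI-FS. Nothing forbids mailing the BDI-FS as well, and 10.4.2 already asks inactive participants for a broader set. A broad request made where possible and a minimum of three instruments can be read as two levels of effort. Missed visits and forms are recorded (10.4.1), and staff stay in contact throughout. Chapters 15 (adverse event reporting) and 23 (analysis) are not in the part available and may supply another reporting route or a denominator rule.

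Most of this stands, and it rules out stronger readings that a reader might infer:

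- That non-attenders are asked only for three questionnaires, or that the BDI-FS is never collected from them. The text supports only that it is not required at the floor.
- That harm is under-counted. This is possible but not established, and it concerns only the event defined by the BDI-FS.
- That the arms are biased against each other because only two of them have directive counseling and devices. Section 10.8 is triggered by moving, deployment and debility, and nothing in the text ties these to arm. As an example, take a true rate of 30% in both arms, with 5% of one arm and 15% of the other at the floor. The rates would be 0.95 × 30% = 28.5% and 0.85 × 30% = 25.5%, but only if unassessed people were counted as event-free. No section available says so. With the number assessed as denominator, both arms show 30%.

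What the objection does not remove is the single missed visit, where 10.4.2 does not yet apply, 10.8 is the only rule, and its minimum omits the form.

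**Conclusion.** A minor but real gap in ascertainment. When a visit cannot be arranged by the routes in 10.8, its minimum set does not require the BDI-FS, and adverse events defined by that screen may go unascertained at the 3, 6, 12 and 18 month visits. Sections 10.8 and 10.4.2 also word the remote set differently and need to be reconciled with each other and with 9.3.2.1.

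The size is unknown. The illustrative 0.6 to 13.7 participants missed per visit rests entirely on assumed shares and on applying the same event rate to those not screened. No difference between arms is shown. The conclusion could soften further if Chapter 15 or 23 provides another route to these events or already fixes the denominator.

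**What to change.** Name the seven-item BDI-FS in the 10.8 minimum set for visits through 18 months, and list the mailed instruments in 10.4.2 so that both sections agree with 9.3.2.1. Leave the mode of collection, and how and when responses are reviewed, to the sponsor. A mailed form keeps the paper format of section 9.2 but is read only on return. A call departs from that format, and the calls in 10.5.2 fall between visits.

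Report BDI-FS-defined adverse events by arm and visit with the number assessed as denominator, and show those not assessed as missing.

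The cost is a line of text in each section, seven more items for remote participants, and possibly a different mode of administration for one screen, which should then be recorded.

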**Table 10.1 Study Visit Schedule****A. Treatment Visits**

Visit Number *	Visit Acronym	Permissible time window
Initial Treatment Visit	(T1)	0 to 2 months after randomization
Second Treatment Visit	(T2)	3 to 5 weeks after T1

**B. Follow-up Visits**

Visit Number *	Visit Acronym	Target time from T1	Permissible time window
Follow-up Visit 1	(F1)	3 months	>10 weeks to 4½ months
Follow-up Visit 2	(F2)	6 months	>4½ months to 9 months
Follow-up Visit 3	(F3)	12 months	>9 months to 15 months
Follow-up Visit 4	(F4)	18 months	>15 months to 21 months
Follow-up Visit 5	(F5)	30 months	>24 months to 36 months
Follow-up Visit 6	(F6)	42 months	>36 months to 48 months
Follow-up Visit 7	(F7)	54 months	>48 months to 60 months

**Table 10.2 Study Visit Schedule**  
Data Collected at Follow-up Visits

**A. Questionnaires and Forms**

Visit	Questionnaires and Forms											
	FM	TQ	TF	TI	BD	FT	DS	HH	FS	PA	LE	EQ
3 mo	✓	✓	✓	✓	✓							
6 mo	✓	✓	✓	✓	✓	✓	✓	✓	✓	✓	✓	✓
12 mo	✓	✓	✓	✓	✓	✓						
18 mo	✓	✓	✓	✓	✓	✓	✓	✓	✓	✓	✓	✓
30 mo		✓	✓	✓								
42 mo		✓	✓	✓								
54 m		✓	✓	✓								

FM Follow-up Medical History Form

DS Digit Symbol Substitution Task

TQ Tinnitus Questionnaire

HH Hearing Handicap Inventory

TF Tinnitus Functional Index

FS State-Trait Anxiety Inventory

TI Tinnitus Handicap Inventory

PA Positive & Negative Affect Schedule

BD Beck Depression Inventory

LE Life Events Checklist

FT Follow-up TRT Interview

EQ EuroQOL

**B. Audiological/tinnitus/hyperacusis (ATH) Measures**

Visit	ATH Evaluation Measures						
	audiometric pure tone	speech recognition threshold	tinnitus pitch match	tinnitus loudness match	loudness discomfort level	word recognition scores	
1 mo (T2)	✓				✓		
3 mo	✓				✓		
6 mo	✓	✓	✓	✓	✓	✓	
12 mo	✓	✓	✓	✓	✓	✓	
18 mo	✓	✓	✓	✓	✓	✓	

---

## Chapter 11

#### 11.1 Introduction

Directive Counseling (DC) is one of the two essential components of Tinnitus Retraining Therapy (TRT). The other essential component is low-level sound or sound therapy (ST). The overall goal of DC is to educate the participant about his or her condition, facilitating the “demystification” of the participant’s tinnitus problem and neutralization of the participant’s negative emotional associations with his or her tinnitus. The Study Audiologist also uses DC to help the Study Participant separate problems related to his or her supra-threshold sound sensitivity (hyperacusis or phonophobia) from the tinnitus condition. The way in which these goals are achieved is through education. Both are considered crucial for the successful management of tinnitus and/or hyperacusis.

In this chapter the components of the initial DC appointment are described, including key points that direct the participant toward habituation of his or her tinnitus. Visual aids include a flip-chart presentation specifically designed for the TRTT and a three-dimensional model of the ear. The visual aids required for the DC session are identified at the point in the counseling session where they are used. These materials serve to pace and guide the counselor through the DC session, insuring that the DC rigor, intensity, and length are equivalent across Study Participants and Clinical Centers.

This chapter also describes the strategies used during follow-up DC sessions.

## **11.2 Initial DC Appointment**

The Study Audiologist must prepare and review all materials needed for counseling before the initial DC session. These materials include the Baseline TRT Interview Form (which is completed at baseline by the Study Participant), the TRT category assigned to the Study Participant at baseline by the Study Audiologist, all audiological/tinnitus/ hyperacusis (ATH) evaluation test data, and the visual aids used during the counseling session. The Study Audiologist is also responsible for ensuring that the visual aids, including the three-dimensional model of the ear and the flip-chart, are ready in advance. The Study Audiologist should also bring a copy of the TRT checklist for the imminent counseling session. S/he should complete Sections A and B before counseling begins and complete the remaining sections during and after the counseling session. Appendix A includes a script and copies of the visual aids, and Appendix B some additional examples that can be used during Directive Counseling.

The voice recorder which is used to monitor the counseling session for quality control should be set up and checked prior to the counseling session to ensure that there are no difficulties or delays associated with this aspect of the study.

During the initial DC session, the Study Audiologist:

- Explains the results of the ATH evaluation;
- Educates the Study Participant about the anatomy and physiology of the normal auditory system;
- Describes how the central auditory system and higher cortical processes may interpret an auditory signal and how this processing relates to the participant's tinnitus perception;
- Describes the Jastreboff model of tinnitus; and
- Sets goals with and for the individual participant.

Each participant is counseled individually, along with any family members who may be present during the session. At the Initial Treatment Visit (T1), which lasts approximately 2 hours, the Study Audiologist systematically presents information designed to help the Study Participant change the way that he or she views his or her tinnitus and/or hyperacusis, addresses the individual participant's concerns, and recommends strategies to help the participant achieve the long-term goal of habituating the awareness of, and annoyance to, his or her tinnitus. Sufficient time is allowed to answer the participant's questions and to ensure that he or she understands all information presented and the treatment goal of reducing the impact of tinnitus in the participant's life.

### **11.2.1 ATH Evaluation**

The first step in a DC session is to review and explain to the participant the results of his or her ATH evaluation. One objective of this review is to help the participant begin to understand and separate his or her hearing status and/or sound tolerance problem from the tinnitus condition. It is necessary to have a copy of the audiogram and other materials generated at the participant's ATH evaluation. These materials may be enlarged using a photocopier for easier viewing and explanation.

During the review of the participant's audiometric results, the Study Audiologist will show the participant the audiogram for each ear separately and explain to the participant how to interpret the pure-tone results and speech-test data. The Study Audiologist then will compare the participant's results to those expected for a normal-hearing person, noting any differences between ears and the relation between the participant's audiometric configuration and history of associated noise trauma or ototoxicity.

The concept and measurement of Loudness Discomfort Level (LDL) are reviewed next. The Study Audiologist describes the test and shows the participant his or her results. These results are then compared with those for someone with normal supra-threshold sensitivity to sound, and also to those for someone with reduced sound tolerance. The Study Audiologist will use the results from the Baseline TRT Interview Form to discuss with the participant how the LDL provides evidence of hyperacusis, phonophobia (i.e., fear of specific sounds), misophonia (i.e., dislike of specific sounds), or normal sound tolerance.

The Study Audiologist next describes the results of the Tinnitus Pitch Match, emphasizing that the pitch obtained may not be an exact match, but rather a "snapshot" of the sound closest in frequency and sound quality to the pitch of the participant's most troublesome tinnitus signal. The Study Audiologist explains that the frequency of the pitch match will vary from participant to participant (and even from day-to-day for a given participant), and that each participant will

describe his or her tinnitus quality differently (e.g., hissing, ringing, buzzing, chirping, etc). The Study Audiologist will emphasize that the pitch match or qualitative type of sound has little or no predictive value for the process of habituation. The Study Audiologist specifically should reinforce the idea that the type of noise or the pitch of tinnitus is meaningless with respect to whether the treatment will be effective, but changes in the qualitative aspects of the tinnitus signal may make it more or less annoying from one day to the next.

Immediately following discussion of the Tinnitus Pitch Match, the Study Audiologist will review the results for the Tinnitus Loudness Match. The loudness of the tinnitus signal is matched to the loudness of the Tinnitus Pitch Match stimulus, which usually is judged by participants to be within 2 to 10 dB of the audiometric threshold of the Tinnitus Pitch Match frequency. The Study Audiologist presents the tinnitus loudness in terms of sensation level (i.e., the number of decibels above the audiometric threshold for the Tinnitus Pitch Match frequency). The Study Audiologist should emphasize that tinnitus is a weak signal in terms of sensation level, despite the fact that it may be annoying or intrusive to the participant. In particular, the Study Audiologist should use care not to minimize the importance of annoyance or intrusiveness of the tinnitus signal to the participant. A neutral statement to use is that, "The physical properties of the tinnitus signal indicate that it is an extremely weak signal in relation to your hearing thresholds; however, this does not mean that the tinnitus is not annoying or intrusive for you." The concept that the tinnitus is a weak signal will be reinforced later in the DC.

Finally, the Study Audiologist reviews the speech tests, explaining that these tests are designed to demonstrate the ability of the participant to detect and understand normal conversational speech. The Study Audiologist explains the speech-tests results, beginning with the speech reception threshold (SRT). The SRT measures the participant's ability to detect two syllable words having equal stress on each syllable (e.g., baseball, hotdog). The SRT result (reported in dB HL) for each ear should agree closely with the pure-tone average (also reported in dB HL) for the audiometric speech frequencies (i.e., 500, 1000, and 2000 Hz).

The word recognition or speech discrimination score (% correct), represents the participant's ability to understand familiar single-syllable words delivered to each ear at an optimum presentation level. The 25-word lists used in measuring word recognition are phonetically balanced and represent the range of speech sounds heard in normal conversation.

---

